# Immediate Loading and Fully Guided Surgery: Single Implants

NCT04061694

Includes: Study protocol, English short version translation from Swedish.

Date of ethical approval: 2015-11-13

Study protocol approved 2015-11-13.

Translation date: 2020-02-04

Study protocol

Prospective non-randomized clinical trial to be conducted in accordance with the Helsinki declaration

of 1975 as revised in 2000.

Study protocol to be sent to was approved by the Regional Ethical Review Board in Lund, Sweden

(Dnr 2015/671).

Patients referred to the Centre of Dental Specialist Care, Malmö to be consecutively considered for

inclusion.

The control group (IL) inclusion of at least 20 patients.

Digital planned, fully guided-surgery and immediate loading group (DIL) inclusion of at least 20

patients.

Power calculation: 80.6%, group size 20.

Inclusion criteria as follows:

1. At least 18 years old.

2. In need of a single-tooth replacement of an incisor, canine or pre-molar in the maxilla.

3. Signed informed consent.

Exclusion criteria as follows:

1. General health contraindications for oral surgery.

2. Inadequate oral hygiene, defined as a full-mouth plaque score of above 25%.

3. In need of bone grafting or ridge augmentation

Immediate loading group (IL)

The control group (IL) 25 immediately loaded (IL) dental implants. Treatment included conventional

surgery, dental implants (Tapered Internal, BioHorizons, Birmingham, AL), immediate loading with

temporary restorations that are fabricated manually immediately after surgery and final restorations in

situ 2 months after surgery.

Digital planned, fully guided-surgery and immediate loading group (DIL)

The DIL group to be subjected to an intraoral scanning of the maxilla and antagonist arch performed

with an IOS (Trios 3, 3Shape A/S, Copenhagen, Denmark). Cone beam computed tomography

(CBCT) (ProMax 3D, Planmeca Oy, Helsinki, Finland) of the implant site.

Guided surgery: Guided surgery software (Implant Studio, 3Shape, Copenhagen, Denmark). The implants to be positioned optimal in relation to a predesign of the prosthetic restoration and thereafter the appropriate implant diameter and length selected for each individualy.

The surgical guides (E-Shell 600 Clear, Deltamed GmbH, Friedberg, Germany), made with additive technology, using a digital light processing (DLP) 3D printer (Vida, EnvisonTEC GmbH, Gladbeck, Germany). Master cylinder sleeve (BioHorizons, Birmingham, AL) incorporated into each surgical guide. The surgical guides to be submitted to cold sterilization according to the material suppliers' guidelines.

The temporary restorations finalised (Dental Designer, 3Shape, Copenhagen, Denmark) according to the intended prosthetic design and 3D printed (E-Dent 400, EnvisonTEC GmbH, Gladbeck, Germany).

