#### Radiographic and soft tissue

Marginal bone loss (MBL) at baseline and 12 months.

Digital intra-oral periapical radiographs (Schick Digital X-ray Sensor, Sirona, Salzburg, Austria) using the long-cone parallel technique.

The marginal bone level measurements to be calibrated using the inter-thread distance of the dental implants (1.00 mm). The Image J software (National Institute of Health, Bethesda, MD) to be used for all measurements.

Implant success and survival evaluated according to Albrektsson et al. 1986/1993 after 12 months.

The gingival index (GI) by Löe and Silness 1963, baseline, 6 and 12 months.

The papilla index by Jemt 1997, baseline, 6 and 12 months.

Change in gingival zenith position and papilla levels measured from intraoral scanning's acquired following delivery of the temporary restoration, completion of the final restoration, and at the 3 and 12 months follow-up visits for DIL. Photographic measuring technique used for the IL group has been described by Gjelvold et al. 2017.

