## Aesthetics

Photographs (Nikon D7000, Nikon Corporation, Tokyo, Japan) are to be taken at definitive crown placement and at the 3 and 12 months follow-up appointments.

Pink esthetic score (PES) according to Fürhauser et al. 2005.

White esthetic score (WES) according to Belser et al. 2009.

Perfect outcome and aesthetic failure considered according to Cosyn et al. 2012.

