# Patient-centred considerations

The validated Swedish version of the Oral Health Impact Profile (OHIP-14) according to Hägglin et al. 2007. Recorded at the following appointments: pre-surgery visit; after two months with the temporary crown; on the 12 months follow-up. The additive score to be used.

Visual analog scales (VAS) used to assess patient perceived aesthetic satisfaction, pain and discomfort. The aesthetic outcome scored by the patients at the same appointments as OHIP-14. Pain

and discomfort scored after the surgery and impression appointments. The patients to mark their decision on a non-numerical 100 mm line ranging from "not at all satisfied, severe pain and severe discomfort = 0" (left) to "very satisfied, no pain and no discomfort = 100" (right). Each response then to be given a numerical value by measuring in millimeters the distance from the left end of the line. For OHIP-14 and VAS the patient are to be given the same oral and written information and then left alone to complete the questioners in private.

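### Does a power figure with no named outcome or assumed difference leave the sample size of this trial unfixed?

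*Protocol*

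**What the plan says.** The opening section of the protocol sets a minimum of 20 patients for each of two non-randomised groups: conventional surgery with immediate loading (IL, the control) and digitally planned, fully guided surgery with immediate loading (DIL). The entire justification is "Power calculation: 80.6%, group size 20". No outcome, difference, standard deviation, event rate, significance level or test goes with it. The same section also gives the IL group as 25 implants.

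The outcomes come later, without ranking. Under Radiographic and soft tissue there are "Marginal bone loss (MBL) at baseline and 12 months", then "Implant success and survival evaluated according to" published criteria, the gingival index, the papilla index, and changes in zenith position and papilla level. Aesthetics adds "Pink esthetic score (PES) according to" a published scale, a white esthetic score, and classifications for perfect outcome and aesthetic failure. Patient-centred considerations adds OHIP-14 and "Visual analog scales (VAS) used to assess patient perceived aesthetic satisfaction, pain and discomfort". Nothing is labelled primary or secondary.

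The title block describes the text: "Includes: Study protocol, English short version translation from Swedish". It gives a translation date of 2020-02-04 next to "Study protocol approved 2015-11-13".

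**The concern.** Power is a property of one comparison under one assumed effect. A percentage and a group size alone leave the reader unable to tell what the trial was sized to detect, or to judge whether that effect was reasonable. Which outcome sizes the trial is a design decision that belongs in the protocol, so its absence cannot simply be put down to an unseen SAP.

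With one power figure and a list of equally ranked outcomes, the 80.6% could later be attached to whichever outcome looks best. A single prespecified test keeps its nominal error rate, but a test picked after the data are seen does not. In a non-randomised comparison, prespecification is one of the few safeguards available, so the gap deserves a check.

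**Working it through.** **Inputs.** Power 0.806 and 20 per group come from the opening section of the protocol. Two-sided alpha of 0.05 and a two-sample comparison of means are assumptions, because the protocol states neither.

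**Reproducing the stated figure.** This cannot be done forwards, since there is no effect to enter. Solving backwards with the normal approximation:

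d = (z for alpha + z for power) × √(2/n)

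- Two-sided: (1.960 + 0.863) × √(2/20) = 2.823 × 0.316 = 0.893.
- One-sided: (1.645 + 0.863) × 0.316 = 0.793.
- The exact t-test calculation gives 0.916 two-sided and 0.808 one-sided.

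For a binary outcome, the same power at 20 per group would need a contrast such as 5% against 42%, 10% against 50%, or 50% against 90%.

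**How far the figure carries.** Two-sided t-test power for other standardised differences:

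| Difference (SD) | 20 vs 20 | 25 vs 20 |
|---|---|---|
| 0.5 | 34% | 37% |
| 0.7 | 58% | 63% |
| 0.8 | 69% | 74% |
| 0.9 | 79% | 83% |
| 1.0 | 87% | 90% |

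The second column takes the 25 IL implants as independent units, which is a further assumption. On that basis 80.6% is reached at 0.866. The stated power therefore fits one large effect and cannot describe every listed outcome. Nothing here shows it to be false for the outcome its authors had in mind.

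**Number of candidate outcomes.** Eleven are scores or measurements: marginal bone loss, gingival index, papilla index, zenith position, papilla level, pink and white esthetic scores, OHIP-14 and three VAS items. Implant success, implant survival, perfect outcome and aesthetic failure bring the total to 15. It is 13 if each of those two pairs counts once. Implant deviation is left out because it is measured in DIL only. That the rest are compared between groups is an inference from the joint examinations under Assessments.

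**Cost of a free choice among the eleven.** If there is no true difference and each is tested at 0.05:

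- Independent outcomes: 1 − 0.95^11 = 1 − 0.569 = 0.431, or 43%.
- Equal correlation of 0.5 (assumed, simulated normal data): 31%.
- Equal correlation of 0.8 (same method): 18%.

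These are the consequences of choosing after seeing the data. Nothing in the protocol provides for such a choice, so they bound a hypothetical misuse and do not measure a defect in a written rule.

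**The date of the text.** The sentence beginning "Photographic measuring technique used for the IL group has been described by" goes on to cite a 2017 source, although approval was in 2015. Because the title block openly gives a 2020 translation date, a reference added in between is unremarkable. It has no bearing on the power line.

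**The case for a change.** The best argument for acting is that the protocol itself chose to publish a power figure and then did not say what it is for. An SAP written later can restate the outcome that sized the trial, but it cannot supply it retrospectively. The remedy would be cheap: one sentence copied from the Swedish original or, failing that, a statement that the inputs cannot be traced and that the DIL against IL comparisons are exploratory.

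The factual part of this stands. The line is incomplete, and no outcome is called primary. What does not stand is the step from an incomplete line in an abridged translation to a fault in the trial's design. A bare power figure is just what a summary would keep. The argument must concede that the figure can be neither confirmed nor refuted and that the full protocol may contain the answer. The exploratory fallback applies only if that full text turns out to be silent, which this document cannot show. The short version also makes no confirmatory claim that would have to be withdrawn.

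**Conclusion.** The observation is accurate but calls for no change. In this short version the 80.6% cannot be tied to an outcome or checked. Assuming a two-sided t-test at 5%, it implies a standardised difference of 0.92 (0.81 if one-sided) at 20 per group, which is consistent with the minimum enrolment stated beside it. No rule in the document is shown to produce a wrong result. The missing inputs are detail that an abridged translation can reasonably drop and that analysts would take from the approved Swedish text. Restoring them would leave enrolment, visits and measurements as they are.

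This conclusion rests on the document's own description of itself as a short version. It does not assert that the Swedish protocol names a primary outcome, only that this text gives no ground for saying it does not. The 43%, 31% and 18% figures would matter only if the leading outcome were picked after the results were known, and the protocol does not say or imply that.

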## Surgery protocol DIL

Implant should be placed into healed bone (at least 4 months after tooth loss) in sites that are free from clinical signs of inflammation/infection.

Prior to surgery a single-preoperative dosage of 2 g amoxicillin.

Installed using a guided surgery kit (BioHorizons, Birmingham, AL), mucosal tissue at the implant site removed with a soft tissue punch from the guided surgery kit, no mucoperiosteal flaps.

The installation torque to be registered for each implant and resonance frequency analysis (RFA), measured as the implant stability quotient (ISQ).

The temporary restorations to be immediately mounted onto the dental implants. Adjust to light centric contact and free from eccentric contacts, make necessary adjustments to approximal contacts points.

Postoperatively: 0.2% chlorhexidine for 14 days.

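### Does stating the healed-site condition only for DIL make the non-randomized comparison with IL unsound?

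*Protocol*

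**What the plan says.** The design is declared at the start of the protocol: "Prospective non-randomized clinical trial to be conducted".

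The criteria shared by both groups say two things about the site. The inclusion criterion is "In need of a single-tooth replacement of an incisor, canine or pre-molar in the maxilla", and one exclusion is "In need of bone grafting or ridge augmentation". The other shared criteria cover age, consent, general health and a full-mouth plaque limit.

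The section Surgery protocol DIL adds: "Implant should be placed into healed bone (at least 4 months after tooth loss) in sites that are free from clinical signs of inflammation/infection".

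The IL group has one short paragraph, which opens "The control group (IL) 25 immediately loaded (IL) dental implants". It then names conventional surgery, the implant system, immediate loading with manually made temporary crowns, and final restorations at two months. It says nothing about healing time or local infection.

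The outcomes compared include "Marginal bone loss (MBL) at baseline and 12 months", as well as papilla and gingival measures and aesthetic scores. The only sample-size statement is "Power calculation: 80.6%, group size 20".

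**The concern.** Time since tooth loss and local inflammation describe the site before surgery. A rule on them decides which sites can receive an implant, so it works like an eligibility criterion wherever it is printed. Without randomization, and with no matching or assignment rule stated, common entry conditions are the main protection for the comparison that this document shows.

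If IL admitted recently lost teeth or inflamed sites and DIL did not, differences in marginal bone change, papilla levels, gingival zenith or the pink aesthetic score could come from the sites and be credited to guided surgery. The blinded examiner described under Assessments protects the measurement but not the make-up of the groups. The grafting exclusion narrows the gap, yet it sets no minimum healing time and does not mention local infection.

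**Working it through.** **1. Is the condition stated for IL anywhere?** No. It appears once, under Surgery protocol DIL. The one outside source cited for an IL procedure, in the section Radiographic and soft tissue, is cited for a photographic measuring technique and not for site selection.

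**2. What else is stated for DIL and not for IL?**

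| Item | DIL | IL |
|---|---|---|
| Site condition | stated | silent |
| Preoperative antibiotic | stated | silent |
| Insertion torque and ISQ | stated | silent |
| Contact adjustment of the temporary crown | stated | silent |
| Postoperative rinse | stated | silent |
| Impression method and crown type for the final restoration | stated | silent |
| Timing of the final restoration stage | two months | two months |

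IL surgery is simply not described in this short version. The missing site rule is one of several blanks with the same cause, so it says nothing particular about how IL sites were chosen.

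**3. Do the two places conflict?** The shared criteria say who may enter, and the DIL section says where the implant is to go. Both can be followed together.

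**4. How large could a bias be?** The document gives no inputs for this, so every share and shift below is assumed.

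Let q be the share of IL sites outside the DIL condition and b the shift in outcome for those sites, in SD units. Then bias = q × b. The lowest non-zero case is 0.10 × 0.5 = 0.05 SD, and the highest is 0.40 × 1 = 0.40 SD. The test is a two-sided t-test at 5%, with 25 IL and 20 DIL sites, one implant per patient and no true difference. Rejection rates for non-zero q come from a simulation of 1,000,000 runs that includes the extra IL variance.

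| q | b (SD) | bias (SD) | false-positive rate |
|---|---|---|---|
| 0 | any | 0 | 5.0% |
| 10% | 0.5 | 0.05 | 5.3% |
| 20% | 0.5 | 0.10 | 6.1% |
| 20% | 1 | 0.20 | 9.2% |
| 40% | 0.5 | 0.20 | 9.7% |
| 40% | 1 | 0.40 | 22.8% |

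The first row is as compatible with the text as any other.

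**5. What would restricting IL to matching sites cost?** The stated 80.6% cannot be reproduced directly, because no effect size, SD, alpha or sidedness is given. Solving backwards with an assumed two-sided t-test at 5%, 80.6% at 20 per group implies a difference of 0.916 SD. At that difference, power is 84.7% with 25 against 20. If 40% of IL sites were dropped, 25 × 0.60 = 15 would remain, and power with 15 against 20 would be 74.0%.

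**The case for a change.** The strongest case for a change is that it is cheap and useful whatever the answer. If one rule covered both groups, a sentence in the shared criteria settles the matter. If not, readers of a non-randomized comparison need to know. Site eligibility belongs in a protocol, an analysis plan can adjust only for what was recorded, and this document does not provide for recording time since tooth loss. Checking charts for about 45 sites is little work.

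Part of this stands. The asymmetry on the page is real, and a line saying whether the site rule also covered IL would help a reader. It does not show that the plan is wrong. The text gives no sign that IL used other sites. The full Swedish protocol, which is not at hand, may state the rule for IL. The IL paragraph is written partly in the past tense with a fixed count of 25 implants. That is compatible with a group already treated, although the document does not say so; if it was, rewording the criteria could not alter who entered. Tabulating site features by group and checking a comparable subset are steps an analysis plan commonly covers, and none is shown here.

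**Conclusion.** No change to the plan follows. The observation is accurate: the site condition is written for DIL and not for IL. It is a gap in an abridged translation that leaves IL surgery undescribed, and not a contradiction or a design that leads to a wrong result. Both groups already share jaw, tooth types, plaque limit and the exclusion of sites needing grafting, which narrows the room for difference without removing it.

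The size of any bias cannot be derived from the document. The illustrative false-positive rates run from 5.0% through a negligible 5.3% to 22.8%, and the upper end needs 40% of IL sites to fall outside the condition and to differ by a full SD. If IL in fact followed the same condition, stating it would alter no result. If it did not, analysts can be expected to describe site status by group and examine the comparable IL sites, accepting a power loss of the order shown. No view is taken here on which site rule is clinically right.

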#### Definitive prosthesis procedure DIL

Two months after surgery, intraoral scanning (Trios 3, 3Shape A/S, Copenhagen, Denmark).

The final screw-retained single implant crown: Titanium base abutment (BioHorizons, Birmingham, AL) and a zirconia crown (BruxZir, Glidewell Labratories, Newport Beach, CA).

All laboratory procedures to be performed by the same team of dental technicians and all prosthetic procedures to be performed by one person.

#### **Assessments**

DIL and IL baseline and follow-up examinations (3 and 12 months) to be conducted by the same person responsible for the prosthetic treatment

Subsequent assessments of radiographs and aesthetics to be performed by an examiner not involved in patient treatment and blinded to patient group allocation.

#### Radiographic and soft tissue

Marginal bone loss (MBL) at baseline and 12 months.

Digital intra-oral periapical radiographs (Schick Digital X-ray Sensor, Sirona, Salzburg, Austria) using the long-cone parallel technique.

The marginal bone level measurements to be calibrated using the inter-thread distance of the dental implants (1.00 mm). The Image J software (National Institute of Health, Bethesda, MD) to be used for all measurements.

Implant success and survival evaluated according to Albrektsson et al. 1986/1993 after 12 months.

The gingival index (GI) by Löe and Silness 1963, baseline, 6 and 12 months.

The papilla index by Jemt 1997, baseline, 6 and 12 months.

Change in gingival zenith position and papilla levels measured from intraoral scanning's acquired following delivery of the temporary restoration, completion of the final restoration, and at the 3 and 12 months follow-up visits for DIL. Photographic measuring technique used for the IL group has been described by Gjelvold et al. 2017.

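### Gingival zenith and papilla-level change is measured from intraoral scans in DIL and from photographs in IL, so method cannot be separated from group in any comparison of this outcome

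*Protocol*

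**What the plan says.** The protocol's section on radiographic and soft-tissue outcomes sets the measurement method by group. For DIL it is "Change in gingival zenith position and papilla levels measured from intraoral scanning's acquired following delivery of the temporary restoration", then at "completion of the final restoration, and at the 3 and 12 months follow-up visits for DIL". The next sentence turns to the control group: "Photographic measuring technique used for the IL group has been described by" a cited publication.

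Other parts of the protocol bear on this:

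- **Opening section.** The trial is non-randomized and IL is its control: "The control group (IL) inclusion of at least 20 patients". DIL has the same minimum.
- **Assessments.** The examination schedule, including an undefined baseline, is common to both groups. Reading is assigned as follows: "Subsequent assessments of radiographs and aesthetics to be performed by an examiner not involved in patient treatment". That examiner is blinded to group.
- **Aesthetics.** Photographs "are to be taken at definitive crown placement and at the 3 and 12 months follow-up appointments". No group limit is attached.

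The protocol describes no method common to both groups for this outcome. It neither states that the outcome will be compared between groups nor limits it to description within each group.

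**The concern.** When one instrument is used only in DIL and another only in IL, the group contrast and the instrument contrast are the same contrast. No later analysis of those readings can separate them, because no patient is planned to be measured for this outcome by both methods and neither group is split between them. A statistical analysis plan could choose the model, but it could not recover the missing information without a common-method reading.

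If a DIL-IL difference were reported from the planned measurements, a difference in scale or projection between scan and photograph could pass for a treatment difference or hide one, in either direction. The point is confined to this outcome. Gingival index, papilla index, PES and WES are listed without group-specific methods.

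**Working it through.** **Methods side by side**

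| | DIL | IL |
|---|---|---|
| Method for zenith and papilla-level change | Intraoral scan | Photographic technique, by citation |
| Other method planned for this outcome | None stated | None stated |
| Photographs under Aesthetics | Definitive crown, 3 and 12 months (no group limit) | Same |

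Method and group coincide completely. The only image source that the protocol schedules without a group limit and that could carry a common method is the photographs.

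**Which errors survive in a change score**

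Suppose a method reads a + k × (true level), where a is a constant offset and k a scale factor. The change between two visits is then k × (true change). The offset a cancels and k does not. If both groups have the same mean true change m, and one method has scale k while the other is exact, the false difference between groups is (k − 1) × m.

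**Size, as an illustration only**

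The protocol gives no scale error, mean change or SD for this outcome. Its power figure (80.6% with 20 per group) names no endpoint or effect size, so it offers nothing to reproduce here.

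- From the protocol: 20 patients per group.
- Assumed: two-sided 5% pooled-variance t-test, SD of true change 1, equal mean m in both groups, no true difference, and scale k in one group only.
- Pooled SD = √((1 + k²)/2).
- Noncentrality = |k − 1| × m / pooled SD × √(20/2).

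Example with k = 0.8 and m = 1: the shift is 0.20, the pooled SD is √(1.64/2) = 0.906, and the noncentrality is 0.20/0.906 × 3.162 = 0.70. The false-positive rate is about 10.5%.

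Simulated false-positive rates (2,000,000 runs each), which the noncentral t calculation reproduces to within 0.1 percentage point:

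| Scale error × mean change (SD) | Cases (k, m) | False-positive rate |
|---|---|---|
| 0.05 | 0.9, 0.5; 1.1, 0.5 | 5.3%; 5.2% |
| 0.10 | 0.9, 1; 1.1, 1; 0.8, 0.5; 1.2, 0.5 | 6.2%; 6.0%; 6.4%; 5.9% |
| 0.15 | 0.9, 1.5; 1.1, 1.5 | 7.8%; 7.2% |
| 0.20 | 0.9, 2; 1.1, 2; 0.8, 1; 1.2, 1 | 10.0%; 9.1%; 10.5%; 8.7% |
| 0.30 | 0.8, 1.5; 1.2, 1.5 | 17.6%; 13.4% |
| 0.40 | 0.8, 2; 1.2, 2 | 27.6%; 20.1% |

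The product drives the result: a 10% scale error with a mean change of 2 SD does about as much harm as a 20% error with a mean change of 1 SD. A constant offset alone leaves the rate at 5%. Projection error and visit-dependent error are not modelled.

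**The case against.** The strongest reply is that nothing in the protocol is wrong as stated. No sentence promises a DIL-IL comparison of this outcome, and an analysis plan that is not at hand may confine it to within-group description. The IL technique is given only by citation. If it yields well-calibrated distances, the scale error could be negligible. Every input to the illustration is assumed. The trial is non-randomized, so any group difference already calls for caution, and this is one soft-tissue measure among many.

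Most of this stands, and it limits the weight of the point without removing it. The assignment of method by group is fixed in the protocol itself. IL is called the control, and nothing restricts this outcome to description. A good calibration in the cited source would make the bias small, but the two methods would still be aliased with group.

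Two stronger readings are tempting and are not supported:

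- **Different starting visits.** A reader might infer that change starts at different visits in the two groups, because the first DIL scan follows the temporary restoration while the first photograph listed under Aesthetics is at definitive crown placement. The protocol does not say that those photographs are the ones used for the IL measurement. It also gives both groups a baseline examination: "DIL and IL baseline and follow-up examinations (3 and 12 months". The reference visit is a detail that the analysis plan or the cited publication may settle, so its absence here is no fault.
- **Bias shown.** A reader might infer that the comparison is demonstrably biased. The protocol gives no basis for a size or a direction.

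**Conclusion.** The point holds as a conditional one. If gingival zenith or papilla-level change is compared between DIL and IL on the measurements as planned, the difference is fully confounded with measurement method and cannot be interpreted as a treatment difference.

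How much this matters is unknown. Under the assumptions above the inflation is negligible while scale error times mean change is about 0.1 SD or less, moderate near 0.2 SD and serious near 0.4 SD. It is a cheap improvement to a single outcome and does not threaten the trial as a whole. Confidence is medium, because the intended use of the outcome and the details of the IL technique lie outside the protocol.

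**What to change.** For any between-group comparison, measure both groups with the same photographic technique on the photographs taken "at definitive crown placement and at the 3 and 12 months follow-up appointments", preferably read by the blinded examiner. Keep the DIL scans, including the one after the temporary restoration, as within-DIL description. If suitable photographs do not exist in both groups, report this outcome within group only and draw no DIL-IL conclusion.

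**Cost.** If the photographs were taken in DIL, as the absence of a group limit suggests, no new visit is needed: 20 patients × 3 photographs = 60 extra readings. This count assumes that IL is already read at those three visits; if it was read at others, IL needs further readings too. The comparison loses the window between temporary and definitive restoration. It also depends on the photographs suiting the cited technique, which the protocol does not show.

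**Optional.** The same 60 readings, set against the DIL scans at the three shared visits, would give a scan-photograph agreement check. With 20 pairs the 95% interval for the mean difference in change has half-width t(0.975, 19)/√20 = 0.47 SD of the paired differences. That can support a common-method comparison but is too imprecise to replace one.
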